## **5.0 Investigational Plan**

### **5.1 Overall Study Design and Plan: Description**

This Phase 2/3, multicenter study will be offered to subjects who received at least one dose of an ABT-493- and/or ABT-530-containing regimen at any dose level in an eligible prior AbbVie Phase 2 or 3 study for the treatment of chronic HCV and elect to enroll in this study. The subject must have completed the follow-up period of the prior eligible AbbVie study.

It is anticipated that approximately 400 subjects will participate in this study. An attempt will be made to enroll all virologic failures who will not receive immediate re-treatment with a regimen containing ABT-493/ABT-530.

At the Day 1 Visit, subjects will provide written (signed and dated) informed consent prior to any study specific procedures being performed. The investigator will evaluate whether the subject meets all of the eligibility criteria specified in Section 5.2.1 and Section 5.2.2 prior to enrollment in this rollover study.

Subjects will be followed for a total of approximately 3 years after their last dose of DAA in the previous HCV clinical study. The 3 years will be inclusive of any post-treatment period in the prior study, as well as any gaps between the end of the prior study and enrollment in this study. Subjects must complete the full post-treatment period of the prior study before enrolling into Study M13-576. Once a subject has reached 3 years post-DAA therapy, participation in this study will be completed, except for subjects enrolled with virologic failure who receive re-treatment with a HCV antiviral regimen other than investigational ABT-493/ABT-530. Subjects who are retreated with investigational ABT-493/ABT-530 are not allowed in this study. Subjects who are re-treated with HCV regimens other than investigational ABT-493/ABT-530 will have only one further assessment for treatment outcome 12 weeks after stopping that therapy or earlier if already known (in cases of treatment failure). (See [Appendix C](#), Table B, Study Activities for Virologic Failures Receiving Re-Treatment).

Subjects who have not been re-treated will return to the study site for their scheduled visits on an outpatient basis as described in Section 5.3.1 until approximately 3 years after their last dose of DAA in the previous clinical study (See Appendix C, Table A, Study Activities for SVR and Non-SVR Subjects Not Receiving Re-Treatment).

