### **5.2.1 Inclusion Criteria**

A subject will be eligible for study participation if he or she meets the following criteria:

1. The subject is male or female 18 years of age or older.
2. The subject has received at least one dose of an ABT-493- and/or ABT-530 containing regimen in a prior AbbVie HCV Phase 2 or 3 study (see Appendix D for list of eligible prior studies).
3. The interval between the last dose of the AbbVie DAA therapy from the previous clinical study and enrollment in Study M13-576 must be no longer than 2 years for subjects who have not been retreated. Subjects who have been treated with a commercially-available anti-HCV treatment may be enrolled greater than 2 years after the last dose of the AbbVie DAA therapy from the previous clinical study.
4. The subject must voluntarily sign and date the informed consent form approved by an Independent Review Board or Ethics Committee prior to the initiation of any study-specific procedures.
5. Subject completed the post-treatment period of an eligible prior study.

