#### **8.1.1 Efficacy**

Efficacy analyses will be conducted in all enrolled subjects as specified above including data up to the last follow-up in this study prior to any HCV re-treatment. The number and percentage of subjects in the full analysis set who maintain SVR in this study will be summarized out of subjects in the full analysis set who achieved SVR12 in the previous study. The number and percentage of subjects who relapse or have new HCV infection will be summarized out of subjects in the full analysis set who achieved SVR12 in the previous study. The time to relapse or new infection from the end of DAA treatment for subjects who achieved HCV RNA < LLOQ at the end of treatment in the previous study will be displayed graphically using Kaplan-Meier curves. Similarly, the time to relapse or new infection from SVR12 time point for the subset of subjects who achieved SVR12 in the previous study will also be displayed graphically using Kaplan-Meier curves. These summaries will be separate for subjects who have probable relapse as distinguished from subjects who have probable new HCV infection based on AbbVie's evaluation of DNA sequence of HCV drug target genes.

For subjects in the full analysis set, HCV RNA measurements taken after the start of another anti-viral HCV treatment (after completion of AbbVie DAA treatments in previous study) will be excluded from the analyses.

A listing of subjects who are re-treated will be provided summarizing HCV treatment regimen and SVR outcome.

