6.2 Definition of Analysis Windows

For efficacy analyses of HCV RNA and resistance, the time windows specified in Table 1 describe how efficacy data are assigned to analysis (or SVR) windows during the Post-Treatment Period of the previous study and in Study M13-576. All time points and corresponding time windows are defined based on the blood sample collection date.

For safety laboratory data collected within Study M13-576, the time windows specified in **Table 2** describe how data are assigned to protocol-specified time points.

If more than one assessment is included in a time window, the assessment closest (except in analyses of SVR) to the nominal time will be used. If there are two observations equally distant to the nominal time, the latest one will be used in analyses. For analyses of SVR, the last value in the window will be used.

If multiple measurements are made on the same day, the average of the values will be used to calculate descriptive statistics, except baseline values (see Section 6.1).

Table 1. Analysis Time Windows for HCV RNA and Resistance Endpoints

[figure not shown]
Scheduled Visit	Nominal Day (Study Drug End Day)	Time Window (Study Drug End Days Range)
Post-Treatment Week 4 (SVR ₄)	28	3 to 56
Post-Treatment Week 12 (SVR ₁₂)	84	57 to 126
Post-Treatment Week 24 (SVR ₂₄)	168	127 to 210
Post-Treatment Week 36	252	211 to 294
Post-Treatment Week 48	336	295 to 378
Post-Treatment Week 60	420	379 to 462
Post-Treatment Week 72	504	463 to 546
Post-Treatment Week 84	588	547 to 630
Post-Treatment Week 96	672	631 to 714
Post-Treatment Week 108	756	715 to 798
Post-Treatment Week 120	840	799 to 882
Post-Treatment Week 132	924	883 to 966
Post-Treatment Week 144	1008	967 to 1050
Post-Treatment Week 156	1092	1051 to 9,999

Note: The result closest to the scheduled time point will be used, except for SVR endpoints, where the last HCV RNA value in the window will be used.

Table 2. Analysis Time Windows for Study M13-576 Protocol Defined Assessments, other than HCV RNA and Resistance

Scheduled Visit	Nominal Day (Study Day)	Time Window (Study Days Range)
Day 1	1	1
Month 3	91	2 to 136
Month 6	181	137 to 271
Month 12	361	272 to 451
Month 18	541	452 to 631
Month 24	721	632 to 811
Month 30	901	812 to 991
Month 36	1081	992 to 9,999

Note: A month is defined as 30 days. The closest value in the window will be used.

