10.2 Efficacy Analyses

The following efficacy analyses will be conducted on the full analysis set including data up to the last follow-up in this study prior to any HCV re-treatment. For subjects in the

[figure not shown]

full analysis set, HCV RNA measurements taken after the start of another anti-viral HCV treatment (after completion of AbbVie DAA treatments in previous study) will be excluded from the analyses.

The number and percentage of subjects in the full analysis set who achieved SVR₁₂ in the previous study will be summarized overall and by study. A listing of subjects in the full analysis set who did not achieve SVR₁₂ will be provided.

Based on the full analysis set, the number and percentage of subjects who maintain SVR in this study among those who achieved SVR₁₂ in the previous study will be summarized, overall and by visit. Study visits will be displayed as Post-Treatment Weeks 24, 36, 48, 60, 72, 84, 96, 108, 120, 132, 144, and 156. For each visit, the denominator will indicate the number of subjects in the full analysis set who achieved SVR₁₂ and have HCV RNA data within the corresponding visit window. For the overall summary, the denominator will indicate the number of subjects in the full analysis set who achieved SVR₁₂. Overall maintenance of SVR is defined as no confirmed HCV RNA ≥ LLOQ after the SVR₁₂ timepoint (from the previous study) through the last HCV RNA measurement in this study. Confirmation of quantifiable HCV RNA values can occur among any two consecutive HCV RNA values; either both during the same visit window or at the end of a visit window and in the next window. The visit window corresponding to the first occurrence of the confirmed HCV RNA ≥ LLOQ will be counted as having the failure. If the last available value in the study is \geq LLOQ, then the subject will be considered as not maintaining SVR (i.e., will not require confirmation). The summary will include the subject number and the visit window corresponding to the first occurrence of quantifiable HCV RNA.

Among the subjects in the full analysis set who achieved SVR₁₂ in the previous study, a listing of subjects who do not maintain SVR will be provided with subject number, previous study number, the reason (relapse or reinfection) for not maintaining SVR, days from study drug end date to relapse or reinfection, and whether the relapse or reinfection occurs before or after enrolling into this study.

[figure not shown]

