The number and percentage of subjects who relapse (see **Relapse**_{late} definition) at any time up to the last follow-up in this study will be summarized out of subjects in the full analysis set who achieved SVR₁₂ in the previous study. In addition, the number and percentage of subjects in the full analysis set who relapsed anytime (see **Relapse**_{overall} definition) or have new HCV infection (see definition of reinfection) anytime will be summarized.

The time to relapse (**Relapse**_{overall}) or new HCV infection (i.e., reinfection) from the end of DAA treatment for subjects who achieved HCV RNA < LLOQ at the end of treatment in the previous study will be displayed graphically using Kaplan-Meier curves. Similarly, the time to relapse (**Relapse**_{late}) or new HCV infection (i.e., reinfection) from the SVR₁₂ time point for the subset of subjects who achieved SVR₁₂ in the previous study will also be displayed graphically using Kaplan-Meier curves. These summaries will be separate for subjects who have probable relapse as distinguished from subjects who have probable new HCV infection (i.e., reinfection) based on the definitions of relapse and reinfection in Section 10.1.

For the first Kaplan-Meier curve among subjects with final on-treatment HCV RNA < LLOQ, time to event will be measured as the number of days from the last dose of study drug (in the previous study) to event or censoring time. Subjects who do not relapse or were not reinfected will be censored at the date corresponding to the last available HCV RNA measurement.

For the second Kaplan-Meier curve among subjects who had achieved SVR₁₂, time to event will be measured as the number of days from the nominal day of SVR₁₂ assessment to event or censoring time. Subjects who do not relapse or were not reinfected will be censored at the date corresponding to the last available HCV RNA measurement.

For both subjects in the full analysis set and subjects excluded from the full analysis set, a listing of subjects who are re-treated will be provided specifying whether the re-treatment occurs before or after enrolling into the study, prior AbbVie regimen, HCV re-treatment regimen, and SVR₁₂ outcome.

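### The SVR12 durability analyses start at nominal Day 84 although enrolment can come about 21 months later and depends on what happened in between; a delayed-entry curve and a before/after-enrolment split should be added beside them

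*SAP*

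**What the plan says.** - **Start of the clock.** SAP 10.2: "Overall maintenance of SVR is defined as no confirmed HCV RNA ≥ LLOQ after the SVR₁₂ timepoint (from the previous study"). For the second Kaplan-Meier curve, "time to event will be measured as the number of days from the nominal day of SVR₁₂ assessment to event or censoring time". The nominal day is Study Drug End Day 84 (SAP 6.2, Table 1).
- **End of the clock.** SAP 10.2: "Subjects who do not relapse or were not reinfected will be censored at the date corresponding to the last available HCV RNA measurement". No entry time, delayed entry or left truncation is mentioned.
- **Enrolment.** Under Protocol 5.2.1, criterion 3, the interval from last DAA dose to enrolment "must be no longer than 2 years for subjects who have not been retreated". Protocol 5.1 makes the 3-year follow-up "inclusive of any post-treatment period in the prior study, as well as any gaps between the end of the prior study" and enrolment here.
- **Who is in the set.** SAP 5.1 removes anyone re-treated before enrolling. Protocol 5.2.2 bars subjects who took investigational HCV therapy after the parent regimen or joined M15-942. Protocol 5.1 says that the study will try to enrol all virologic failures not going straight to ABT-493/ABT-530 re-treatment.
- **What is measured before enrolment.** The parent post-treatment period must be complete (Protocol 5.2.1). Late relapse and overall SVR use HCV RNA from both studies (SAP 10.1). A sample is drawn at Day 1 (Protocol Appendix C, Table A). A relapse or reinfection before enrolment counts as a failure and is flagged as such in a listing (SAP 10.2).
- **Endpoint wording.** Protocol 8.1.1 summarises "The number and percentage of subjects in the full analysis set who maintain SVR in this study", out of those in the set with SVR12.

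**The concern.** An SVR12 achiever is counted at risk from Day 84 but can join the analysis set only at Day 1. Whether that subject joins can depend on the outcome being measured. Someone who relapsed or was reinfected in between and took a commercial regimen drops out of both numerator and denominator. Someone who stayed aviraemic is kept, with all the earlier time counted. In the other direction, recruitment aims at untreated virologic failures; if that covers relapse after SVR12, such subjects may enrol more readily than others.

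Durability of response is a primary objective, and few events are likely. The overall maintained-SVR percentage and the SVR12 curve may then partly describe who was available to enrol. The planned tables do not let a reader judge this: the before/after-enrolment flag appears only in a listing, and SAP 8.0 counts follow-up only from the last parent-study dose.

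**Working it through.** The documents give no event rate, power or sample-size figure to reproduce, so the check has two parts.

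**1. Length of the interval (document figures; 2 years = 730 days, 3 years = 1,095 days)**
- SVR12 to latest enrolment: 730 − 84 = 646 days; 646 / 30.5 = 21.2 months.
- SVR12 to 3 years: 1,095 − 84 = 1,011 days. Largest pre-enrolment share: 646 / 1,011 = 64%.
- The part without scheduled sampling is shorter. The length of the parent post-treatment period is not stated. If it was 24 weeks (assumption; Day 168), the gap is at most 730 − 168 = 562 days = 18.4 months, or 562 / 1,011 = 56%.

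**2. Effect on the percentage (assumptions, not from the documents)**

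Assume a constant late relapse or reinfection hazard h, entry uniform from Day 84 (or Day 168) to Day 730, and follow-up to Day 1,095. Let r be the chance that a subject with a pre-enrolment event enters the full analysis set, relative to other subjects.

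- True risk: F = 1 − exp(−h × 1,011 days).
- Risk of a pre-enrolment event: P = the average of 1 − exp(−h × (entry day − 84)) over entry days.
- Planned percentage = (rP + F − P) / (rP + 1 − P).

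At 1% per year with entry from Day 84, F = 2.73% and P = 0.88%:
- r = 0: (0.0273 − 0.0088) / (1 − 0.0088) = 1.87%
- r = 0.5: (0.0044 + 0.0185) / (0.0044 + 0.9912) = 2.30%
- r = 1: 2.73%
- r = 1.5: (0.0132 + 0.0185) / (0.0132 + 0.9912) = 3.16%

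| Entry from | True | r = 0 | r = 0.5 | r = 1 | r = 1.5 |
|---|---|---|---|---|---|
| Day 84 | 2.73% | 1.87% | 2.30% | 2.73% | 3.16% |
| Day 168 | 2.73% | 1.75% | 2.24% | 2.73% | 3.21% |

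For rare events the relative error is close to (r − 1) × the mean pre-enrolment share of the clock. That share is (407 − 84) / 1,011 = 32% for entry from Day 84, and (449 − 84) / 1,011 = 36% for entry from Day 168. So r = 0 understates the risk by about 32% to 36%, r = 0.5 by about 16% to 18%, and r = 1.5 overstates it by about the same. These relative errors hardly change at 0.5% or 2% per year.

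In counts, if all 400 planned subjects had SVR12 (they will not), 1% per year gives 400 × 2.73% = 10.9 true events against 400 × 1.87% = 7.5 at r = 0. At 0.5% per year it is 5.5 against 3.8.

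**Delayed entry.** In a simulation of 1,000,000 subjects at 1% per year with entry from Day 84, a curve with risk-set entry at Day 1 and only later events gave 2.70% against 2.73%, whatever share of pre-enrolment events was lost. With entry from Day 168 it gave 2.53%. Nobody is at risk earlier, so it estimates risk from Day 168 on: 1 − exp(−0.01 × 927 / 365.25) = 2.51%.

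**The case against.** The strongest reply is that most of the interval is not hidden. Parent-study HCV RNA is used, Day 1 brings a new sample, no eligibility criterion excludes viraemic subjects, and pre-enrolment failures count. By-visit percentages need a value in the window, the overall endpoint is a proportion without person-time, and the protocol says openly that its 3 years include the gap. Subjects excluded from the set, and those re-treated, are listed.

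Much of this stands. A reader might infer that all pre-enrolment time is unobserved and credited as event-free. The documents do not support that: only the gap between the end of the parent study and Day 1 lacks sampling, and untreated viraemia persisting to Day 1 would be found and counted in those who enrol, though dated late. A reader might also infer that the bias must flatter durability. Active recruitment of untreated failures could push the other way, and there is no bias in the percentage if entry is unrelated to outcome.

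What does not stand is that these safeguards remove the problem. A Day 1 sample says nothing about subjects who were re-treated first or never enrolled, and a listing of exclusions does not correct the curve.

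**Conclusion.** The point holds as a cheap improvement. The overall percentage and SVR12 curve count subjects from Day 84, while entry to the set depends partly on what happened before Day 1. The relative error runs from about a third too low (all pre-enrolment events lost), through zero (none lost), to too high if failures enrol more readily. The 646 days and 64% come from the documents. The hazard, uniform entry and entry probabilities are assumptions. No hypothesis is tested, so no error rate is affected.

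A reader might go further and replace the primary percentage with post-Day 1 events among subjects below LLOQ at Day 1. That is not supported. Protocol 5.3.2 defines the outcome as relapse or new infection at any time up to last follow-up among enrolled SVR12 achievers. The replacement would also look too favourable whatever the selection. At an assumed 0.5% per year with entry uniform over months 6 to 24, mean follow-up after Day 1 is 36 − 15 = 21 months, so the percentage is about 0.5% × 1.75 = 0.87%. The risk over the full clock is 1.37%.

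**What to change.** Keep the planned primary percentage and Kaplan-Meier curves. In SAP 10.2 add:

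1. An SVR12 Kaplan-Meier curve with time since SVR12 as the axis, risk-set entry at the M13-576 Day 1 date, subjects with HCV RNA < LLOQ at Day 1, and post-Day 1 events only. Label it as conditional on being event-free at the earliest entry time.
2. A table of relapse and reinfection before and after Day 1, from the flag already planned for the listing.
3. The number of SVR12 achievers excluded from the full analysis set for re-treatment before enrolment.

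In SAP 8.0, summarise follow-up from Day 1 beside follow-up from last dose.

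The cost is SAP wording and one entry-time variable; the dates are already held. The price is small early risk sets, no information before the earliest entry, and a shorter stated prospective follow-up. Subjects who never enrolled remain uncounted, but the added curve does not depend on whether subjects with pre-enrolment events entered.

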10.3 Resistance Analyses

The following subjects in the full analysis set will have resistance testing conducted: (1) those with on-treatment virologic failure (VF) in the previous study; (2) those with post-treatment relapse prior to enrollment in Study M13-576; and (3) those who become viremic (with HCV) during Study M13-576.

For all subjects entering Study M13-576 who meet the criteria for resistance testing above (i.e., have virologic failure), listings will be provided to summarize HCV subtype, time of VF, HCV RNA levels, time point(s) sequenced, and assessment of possibility of new infection.

Only samples with an HCV RNA level of \geq 1,000 IU/mL will undergo sequence analysis in order to allow accurate assessment of the products of amplification. For subjects who experience VF before or during Study M13-576, the sample closest in time after the failure with an HCV RNA level \geq 1,000 IU/mL will be used if the HCV RNA level at the time of VF is < 1,000 IU/mL.

The regions of interest for next-generation sequencing (NGS) from all evaluated time points in this study are those encoding complete NS3/4A and/or NS5A (based on regimen received in the earlier study). Subtype-specific prototypic reference strains for sequence analyses will be utilized.

For each DAA target, signature amino acid positions and a key subset of amino acid positions are listed in Table 3. Appropriate subtype-specific prototypic reference sequences will be used for comparison with sequences from samples.

[figure not shown]
[figure not shown]

Table 3. Signature Amino Acid Positions and the Key Subset of Amino Acid Positions

Target	Signature Amino Acid Positions	Key Subset of Amino Acid Positions
GT1 NS3	36, 43 (GT1a only), 54, 55, 56, 80, 107, 122, 132 (GT1a only), 155, 156, 158, 168, 170, 175 (GT1b)	155, 156, 168 (all GTs)
GT 2-6 NS3	36, 43, 54, 55, 56, 80, 155, 156, 166 (GT3 only), 168	-
GT1 NS5A	24, 28, 29, 30, 31, 32, 54 (GT1b only), 58, 62, 92, 93	24, 28, 30, 31, 58, 92, 93 (all GTs
GT 2-6 NS5A	24, 28, 29, 30, 31, 32, 58, 92, 93	-

The following definitions will be used in the resistance analyses:

- Baseline sample: sample collected before the first dose of DAA study drug in the previous study.
- Baseline polymorphism: a polymorphism by NGS in a baseline sample (≥ 2% or ≥ 15% prevalence within a subject's viral population depending on polymorphism frequency threshold utilized) that was not present in the appropriate prototypic reference amino acid sequence for a given DAA target (NS3/4A or NS5A).
- Polymorphism/substitution at a signature amino acid position: polymorphism (relative to reference) present in a baseline sample or substitution (relative to baseline) present in post-baseline sample at a signature amino acid position.
- Post-baseline substitution: an amino acid substitution in a post-baseline time point sample that was not detected at baseline (< 2%) in the subject and is detectable in ≥ 2% of the sequences from the post-baseline sample.
- Enriched substitution: substitution present in both the baseline and a post-baseline sample whose prevalence in the post-baseline sample is at least 20 percentage points greater than the prevalence in the baseline sample [(post-baseline % baseline %) ≥ 20].
- Treatment-emergent substitution: A post-baseline substitution or an enriched substitution.

• Substitution at signature amino acid position: Substitution in a post-baseline sample observed at ≥ 2% prevalence within a subject's viral population that was not present in the appropriate prototypic reference amino acid sequence for a given DAA target (NS3/4A or NS5A).

For subjects with virologic failure who have resistance testing conducted:

- A listing by subject of all baseline polymorphisms (2% detection threshold) at signature amino acid positions will be provided for each DAA target (NS3/4A and NS5A).
- A listing by subject and time point of all treatment-emergent substitutions relative to the baseline amino acid sequences will be provided for each DAA target (NS3/4A and NS5A).
- A listing by subject and time point of all post-baseline substitutions at signature amino acid positions relative to the appropriate subtype-specific reference amino acid sequence will be provided for each DAA target (NS3/4A and NS5A).

